## **8) Risks to Subjects\***

Because of its intestinotrophic mechanism of action, teduglutide may theoretically increase the risk of neoplastic growth, though this has never been proven in clinical trials. For this

IRB Study Number: 20170189  
Version Date: June 16, 2021  
PI: [name]

NCT02889393

reason, patients with evidence or suspicion of active gastrointestinal malignancy will not be enrolled. Abdominal computed tomography scans obtained during the course of routine clinical care will be reviewed for evidence of gastrointestinal malignancy and any patients with concerning findings (as described by the final Radiologist's interpretation) will be excluded. Additionally, patients with a familial history of intestinal malignancy (gastric, small intestine, colon) will be excluded.

For patients meeting American College of Gastroenterology (ACG) colon cancer screening criteria based on age (age 50, or age 45 years in African Americans) who have not had a negative colonoscopy in the 5 years preceding study enrollment, a screening **CT colonography** will be offered. All enrolled patients will be advised of the potential for acceleration of neoplastic growth included in the Gattex (teduglutide) label's Warnings and Precautions, as well as the recommendation for colonoscopy with removal of polyps prior to initiating treatment with Gattex. CT colonography will be offered as an alternative method of screening. Patients with abnormal findings concerning for malignancy will be excluded.

Additional possible safety risks with teduglutide identified in the previous trials also include gastrointestinal obstruction; gallbladder, biliary tract, and pancreatic disease; increased absorption of fluids leading to fluid overload in patients with cardiovascular disease; and increased absorption of oral medications with narrow therapeutic index.

**The grades of adverse events described below are taken from the National Cancer Institute (NCI) Common Terminology Criteria for Adverse Events (CTCAE) v.3.0.**

Intestinal obstruction occurred in 3.9% (n=6) of patients receiving teduglutide in the prior studies, with an onset between 6 days and 19 months. Only 1 patient required surgical intervention. Subjects will be monitored clinically for signs and symptoms of GI obstruction. For those patients who develop obstruction, teduglutide will be temporarily discontinued while the patient is clinically managed and restarted when the obstructive presentation resolves, if clinically indicated.

Biliary symptoms of cholecystitis and gallstones/sludge occurred in 7.5% (n=13) of patients in previous teduglutide studies, though almost half of them had a history of biliary disease prior to enrollment. None of the biliary events necessitated study withdrawal.

Pancreatitis developed in 1.7% (n=3) of all teduglutide-treated patients in previous trials, though all three patients had a history of pancreatitis prior to enrollment. None of the events required study withdrawal.

Fluid overload developed in 13.3 % (n=23) of all teduglutide-treated patients in pooled Phase III studies. Subjects will be closely monitored for increased oral medication absorption, particularly opioids and sedating medications. Subjects will be assessed for pinpoint pupils and lethargy. If clinical evidence of increased oral medical absorption is

IRB Study Number: 20170189  
Version Date: June 16, 2021  
PI: [name]

NCT02889393

discovered, the doses will be accordingly decreased. If clinical evidence of fluid overload is discovered (such as breathlessness, subjective dyspnea, new-onset pitting peripheral edema, change in body weight, and rales on lung auscultation), then EN and PN prescription will be decreased accordingly.

During weekly assessments, if the patient is on PN and there are clinical signs or suspicion of fluid overload, the PN volume will be decreased by 10% to 30% in coordination with the PN Pharmacy. We will then continue monitoring and adjust PN/IV volume accordingly to maintain clinical nutrition and volume status.

Criteria for discontinuation of teduglutide in patients who experience fluid overload include: decrease in room-air oxygen saturation > 5% from baseline, significant worsening of peripheral edema resulting in functional limitation, severe dyspnea resulting in functional limitation, and hospitalization for congestive heart failure.

Because of the laboratory safety monitoring, the subjects will require blood draws before teduglutide initiation, at the mid-point of treatment (week 4), after the completion of the 8 week trial, and at long-term follow up (3 months after end of treatment). Patients with persistently abnormal laboratory results and ongoing adverse reactions will be followed until resolution and will undergo repeat laboratory testing as necessary to ensure resolution of all abnormal laboratory results potentially attributable to study drug. For patients receiving parenteral nutrition, this will not impact them as they will be getting test performed as part of routine care. However, for patients not requiring parenteral nutrition, this entails additional minimal blood loss and the discomfort of needle stick.

The most common adverse events identified in the previous trial (Jeppesen 2012, Teduglutide reduces need for parenteral support among patients with short bowel syndrome with intestinal failure) are mild and related to gastrointestinal symptoms such as abdominal pain (31%), nausea (29%), and abdominal distension (21%).

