### **Eligibility Screening Visit(s):**

Screening procedures can be completed over several visits

Obtain informed consent

Demographics

Medical and surgical history

Review prior and concomitant medications

Collect Physical exam

Collect Vital signs measurements

ECG

Chemistry Panel (sodium, potassium, chloride, bicarbonate, blood urea nitrogen, creatinine glucose) if not done in the last 90 days

Liver Function tests (total bilirubin, direct bilirubin, alkalkine phosphatase, alanine aminotransferase, aspartate aminotransferase, lipase, amylase) if not done in the last 90 days

Serum pregnancy test if applicable

Collect Concomitant medical review

Collect Nutritional assessment

3-day average fistula output

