#### **Data Fields**

Age

BMI

Gender

Charlson Comorbidity Index

Questionnaires (see additional documents)

Cause of major intestinal resection: trauma, emergency operation, elective operation, inflammatory bowel disease, other

Location of fistula: stomach, duodenum, jejunum, ileum, colon

Days since last operation

Days since fistula diagnosis

Type of nutrition: per os (PO), enteral nutrition (EN), parenteral nutrition (PN), PO + EN, PO + TPN, EN + PN, PO +EN + PN

IRB Study Number: 20170189  
Version Date: June 16, 2021  
PI: [name]

NCT02889393

Concomitant medications: antidiarrheals, antisecretory agents  
3-day average fistula volume (continuous variable)  
Output of fistula >500 mL/day (Y/N)

Because of the expected increase in luminal absorption, subjects will be closely monitored for increased oral medication absorption, particularly opioids and sedating medications. Subjects will be assessed for pinpoint pupils and lethargy. If clinical evidence of increased oral medical absorption is discovered, the doses will be accordingly decreased. If clinical evidence of fluid overload is discovered (such as breathlessness, subjective dyspnea, new-onset pitting peripheral edema, change in body weight, jugular venous distention, and rales on lung auscultation), then EN and PN prescription will be decreased accordingly.

Additionally, subjects will be monitored for clinical evidence of volume depletion. Clinical signs suggestive of volume depletion include dry mucus membranes, poor skin turgor, decreased urine output, or rapid body weight loss.

Fluid and volume status will be assessed according to the usual clinical signs and symptoms: breathlessness, subjective dyspnea, new-onset pitting edema, change in body weight, and rales on lung auscultation. This will be assessed both in person at the time of study visit as well as by self report from the subject during phone calls.

Criteria for discontinuation of teduglutide in patients who experience fluid overload include: decrease in room-air oxygen saturation > 5% from baseline, significant worsening of peripheral edema resulting in functional limitation, severe dyspnea resulting in functional limitation, and hospitalization for congestive heart failure.

Data will be de-identified and stored on password-protected network accessible only to research staff. Data will be retained for at least six years following conclusion of the study on this network.

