	Open-Label Extension (up to 12 additional Study Visits and 12 additional Telephone Calls)		
	Extension Study Visit 1 +/- 1 week	Extension Study Telephone Call 1 to End ± 4 d	Extension Study Visit 2 to End +/- 1 week
Informed Consent	X		
Collect Complete Physical Exam Results A	X		X
Collect vital signs measurements B	X		X
Self-administration of medication and teaching if needed	X	X	X
IP Dispensation and Accountability	X		X
Collect chemistry panel results **	X		X
Collect liver function test results **	X		X
Collect serum pregnancy test (if applicable)	X		X
Monitor SAE/AE C	X	X	X
Collect concomitant medication review	X	X	X
Nutritional assessment D	X	X	X
Approx. average daily fistula output	X	X	X
Questionnaires			X F

A. A complete physical examination during an applicable study visit will include an assessment as per clinical judgement.

B. Vital sign measurements during an applicable study visit will include body temperature, heart rate, respiratory rate, and blood pressure. Height will be obtained at Screening only; weight will be measured at screening and during applicable study visits.

C. Patients will be monitored for non-serious adverse events and serious adverse events from the time when informed consent is obtained at Screening up to and including 30 days for SAEs and through the Long Term Follow Up (Study Visit 11) for AEs.

D. May include adjustment of parenteral nutrition (PN) volume as per pre-defined weaning protocol.

E. IP accountability only at visit 10

F. Questionnaires for the Open-Label Extension Study will only be administered at the End of the study

\* PK = Pharmacokinetics, processed according to separate "Sample Processing Procedure"

\*\* Laboratory test results for the Open-Label Extension Study may be collected every 3 months if completed clinically

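### Stopping teduglutide for fluid overload can turn on a fall in oxygen saturation from baseline, but the protocol schedules no saturation reading and does not define baseline

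*Combined protocol and SAP*

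**What the plan says.** The fluid-overload stopping criteria appear twice. Section 6 (Data Fields) has: "Criteria for discontinuation of teduglutide in patients who experience fluid overload include: decrease in room-air oxygen saturation > 5% from baseline". Section 8 (Risks to Subjects) repeats the list, again with "decrease in room-air oxygen saturation > 5% from baseline" as its first item. The other three criteria are worsening edema that limits function, severe dyspnea that limits function, and admission for congestive heart failure.

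The measurements are set out elsewhere. Appendix E, footnote B, reads "Vital sign measurements during an applicable study visit will include body temperature, heart rate, respiratory rate, and blood pressure", and continues "Height will be obtained at Screening only; weight will be measured at screening and during applicable study visits". The screening list in section 5 has only the generic entry "Collect Vital signs measurements". Footnote A says of the examination: "A complete physical examination during an applicable study visit will include an assessment as per clinical judgement".

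Section 6 bases the assessment of fluid status on "breathlessness, subjective dyspnea, new-onset pitting edema, change in body weight, and rales on lung auscultation. This will be assessed both in person" at study visits, "as well as by self report from the subject during phone calls". Saturation is not in that list.

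**The concern.** A change-from-baseline criterion works only if the baseline exists. A site that follows the visit lists and footnote B will start a subject on drug with no room-air saturation on file. If that subject later becomes breathless, a reading can be taken then, but the protocol assures nothing to compare it with, and a missed pre-treatment value cannot be recovered.

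The saturation fall is also the only one of the four criteria with a numeric threshold. Two of the others depend on a judgement of functional limitation, in an open-label trial, and the fourth is a hospital admission. Fluid overload is no remote possibility: section 8 gives 13.3% for it, against 7.5% for biliary events, 3.9% for obstruction and 1.7% for pancreatitis.

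**Working it through.** The documents give no figure to reproduce. The check compares what the criterion needs with what the protocol collects.

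**1. What the criterion needs.** A baseline room-air saturation B and a later value S. The text leaves two readings of the threshold:
- percentage points: S < B − 5
- relative: S < 0.95 × B

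The two cut-offs differ by 0.95B − (B − 5) = 0.05 × (100 − B) points. At an assumed B of 90 that is 0.5 point. The ambiguity is small but should be settled. Neither form can be evaluated without B.

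**2. What the protocol collects.**
- Screening, Enrollment and Visits 1 to 10 (section 5): vital signs are listed, with their content set by footnote B as temperature, heart rate, respiratory rate, blood pressure and weight, plus height at screening. No saturation.
- Telephone calls: no vital signs; fluid status is self-reported.
- Visit 11: no vital signs in section 5 or in Appendix E.
- Extension visits: vital signs are listed, but the visits may be virtual. No saturation.
- Appendix E schedule rows: none for saturation or oximetry.
- Data Fields (section 6): none for saturation.

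Count: 2 mentions as a stopping criterion, 0 as a scheduled measurement.

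**3. Which reading would be baseline.**
- Teduglutide-first subjects start drug after Enrollment, so Screening or Enrollment could serve.
- Standard-of-care-first subjects start at Visit 5, day 56, which is 56/7 = 8 weeks later. Enrollment may itself follow consent by up to 2 months. Taking 2 months as 60 days, a screening value could be about 60 + 56 = 116 days old at first dose.
- Extension subjects may be offered drug at end of treatment or at long-term follow-up, and the latter visit has no vital signs. Nothing says whether the earlier baseline carries over.

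**4. How often it might matter (illustration only).** Section 8 gives 23 cases at 13.3%, so about 23/0.133 = 173 treated patients. If that risk applied unchanged to 10 subjects:
- expected cases: 10 × 0.133 = 1.3
- chance of at least one: 1 − 0.867^10 = 76%

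If the 13.3% reflects 24 weeks of treatment (the length of the Phase III studies described in section 3), with constant hazard, then 8 weeks is one third of the exposure:
- chance of at least one: 1 − 0.867^(10/3) = 38%

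The documents do not give the pooled exposure, and extension treatment would raise the lower figure. Both are chances of any fluid overload. The chance of a case in which saturation alone would decide stopping cannot be derived from the documents.

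**The case against.** The best reply is that the protocol does not prevent the measurement. Footnote B says what vital signs will include, not that nothing else may be recorded, and footnote A leaves the examination to judgement. A reading can be taken at any in-person visit, and hospital care may supply one. The criterion also applies only once fluid overload is present, which is detected from symptoms, edema, weight and rales, so taking a reading on suspicion fits the sequence. This stands, and it weakens the complaint about on-treatment values. It does not supply a pre-treatment value for every subject, so the missing baseline is the firmer part of the point.

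A reader might infer that the criterion can never be triggered, or that no objective stopping rule remains. The documents support neither. Unscheduled readings are allowed, and admission for heart failure is a verifiable event. Section 9 separately allows withdrawal for uncontrolled cardiac dysfunction, an unalleviated drug-related serious event, a significant adverse event or an investigator decision. Nor do the documents show that stopping would come later as a result.

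The 76% should not be read as a forecast. It carries a pooled Phase III rate to a different population treated for 8 weeks. Section 8 links this risk to cardiovascular disease, and section 4 excludes unstable angina, active ischemia and ECGs that suggest heart failure or cardiac disease.

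**Conclusion.** The point holds as an inconsistency inside a safety rule. One of the four fluid-overload stopping criteria depends on a measurement that the protocol does not schedule at baseline or on treatment, so it cannot be applied from protocol-specified data. It could still be applied where readings happen to exist. The other three criteria and the section 9 withdrawal provisions work as written, and the efficacy endpoint, randomization and analysis are not touched.

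Baseline is undefined for subjects who start drug at Visit 5 and for those in the extension. The form of the 5% is also unstated, though its numerical effect is small.

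The conclusion rests on the text alone and needs no assumed event rate. The 38% to 76% range for at least one fluid-overload case is illustrative. It assumes that the pooled Phase III rate carries over, with or without scaling for exposure.

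**What to change.** Reconcile the stopping criteria in sections 6 and 8 with footnote B and the Appendix E schedule, so that the measurement the criterion depends on is collected before first dosing and at the in-person visits where vital signs are already taken. Vital signs are listed at Screening, Enrollment and Visit 5, so a pre-dose reading is possible in both sequences without a new visit.

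The investigators should also state:
- which reading is baseline, for each treatment sequence and for subjects entering the extension, including those who enter at long-term follow-up and those seen virtually;
- whether the 5% is a relative change or percentage points.

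The threshold, the definition of baseline and the stopping rule itself are for the investigators to decide.

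The cost is one line in footnote B, one case report form field and a small amount of added data collection.

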### **9) Adverse Event (AE) Definition**

An AE is defined as any untoward medical occurrence in a subject or clinical investigation subject administered a pharmaceutical/medicinal product. An AE does not necessarily have to have a causal relationship with this treatment.

An AE can therefore be any unfavorable and unintended sign (including a clinically significant abnormal laboratory finding, for example), symptom, or disease temporarily associated with the use of a medicinal product (investigational or marketed), whether or not considered related to treatment with the medicinal product.

An AE includes:

- An exacerbation of a pre-existing illness, sign, symptom, or clinically significant (as determined by the investigator) laboratory test abnormality
- An illness, sign, symptom, or clinically significant laboratory abnormality that is detected or diagnosed after study drug administration

IRB Study Number: 20170189  
Version Date: June 16, 2021  
PI: [name]

NCT02889393

- Pretreatment or post-treatment events that occur as a result of protocol-mandated procedures

An AE does not include:

- The disease or disorder being studied or signs and symptoms associated with the disease or disorder, unless there is worsening of the condition of the disease or disorder
- A pre-existing disease or condition, present at the start of the study, that does not worsen.

Although an overdose of the study drug or concomitant medication without any clinical sign or symptom is not technically an AE, it will be captured as an AE to provide valuable safety data on higher untested doses of study drug.

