### **Enrollment within 2 months of signing consent**

Inclusion/Exclusion criteria

Vital signs measurements

Nutritional assessment

3-day average fistula output

Complete questionnaires (see additional documents):

1. ASCQ-Me Short Form v2.0 - Social Functioning Impact
2. ASCQ-Me v2.0 - Sleep Impact Short Form

IRB Study Number: 20170189  
Version Date: June 16, 2021  
PI: [name]

NCT02889393

3. Global Health Scale v1.2
4. PROMIS Scale v1.0 - GI Belly Pain
5. PROMIS Scale v1.0 - GI Diarrhea
6. PROMIS Scale v1.0 - GI Nausea and Vomiting
7. PROMIS SF v2.0 - Ability to Participate

Teaching of self-administration of medication

After study enrollment, the subject will be randomly assigned (by a computerized method, using the site 'www.sealedenvelope.com') to begin teduglutide treatment immediately or to continue standard of care (SOC) treatment. The randomization will be performed by a member of the study that is not involved in the informed consent process, and will be enclosed in sequentially numbered opaque envelopes. The envelopes will be given to the PI prior to the enrollment visit. At study visit 5 (day 56), the subject will then cross-over to the opposite treatment assignment. The half-life of teduglutide is 2-3 hours. During the period the subjects are on the "SOC only" treatment arm, the subjects will be given the option to replace some Study visits with Telephone Calls for their convenience. If study visits overlap due to the time window, either visit may be skipped or completed on the same day. Please see information below, and the Study schema.

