### **Procedures for Reporting Adverse Events**

Adverse events may be spontaneously reported, obtained through non-leading questioning, or noted during examination of a subject. Adverse events will be recorded from the signing of informed consent through the last dose of study drug. Serious adverse events will be recorded from the signing of informed consent through 30 days after the last dose of study drug.

At each visit, new AEs are recorded sequentially on the Adverse Event log. The AE term will note the diagnosis whenever possible, not the individual signs or symptoms (eg., myocardial infarction will be recorded rather than chest pain, elevated cardiac enzymes, and abnormal ECT). Also recorded are:

- Start and stop date and time
- Whether or not the event is continuing
- Frequency (intermittent, continuous)
- Intensity (mild, moderate, severe)
  - Mild: usually transient, requiring no special treatment and generally not interfering with usual daily activities
  - Moderate: usually ameliorated by simple therapeutic maneuvers and impairs usual activities
  - Severe: requires vigorous therapeutic intervention and interrupts usual activities. Hospitalization may or may not be required.
- Relationship to study drug (not related, related): identify relationship as “related” if a causal relationship between the investigational product and an AE is at least a reasonable possibility (i.e. the relationship cannot be ruled out).
- Whether or not the AE is serious (i.e. an SAE). If identified as an SAE, the AE will be reported as an SAE.
- Actions taken (none, study drug dose interrupted, study drug discontinued, other medication change, non-drug therapy, change in parenteral nutrition or IV fluids).
- Outcome (resolved, severity or frequency increased, ongoing, fatal). An individual AE receives only one outcome.

IRB Study Number: 20170189  
Version Date: June 16, 2021  
PI: [name]

NCT02889393

Adverse events not resolved at the end of treatment will be followed until resolution or until the AE is judged by the investigator to have stabilized.

✓

Laboratory values, blood pressure, ECG evaluations, and clinical findings at the scheduled physical examinations will be reported as AEs if they:

- Are considered clinically significant by the investigator
- Fulfill SAE criteria, and/or
- Cause subject discontinuation from the study

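### The adverse event definition ties new illness to study drug dosing, which does not fit the SOC-first sequence and conflicts with recording from consent

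*Combined protocol and SAP*

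**What the plan says.** **What an AE is (section 9, Adverse Event (AE) Definition).** The lead sentence reads: "An AE is defined as any untoward medical occurrence in a subject or clinical investigation subject administered a pharmaceutical/medicinal product". The next paragraph widens this to findings "associated with the use of a medicinal product (investigational or marketed), whether or not considered related to treatment with the medicinal product". Three items are then listed as included:

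- Worsening of something already present, with no condition on dosing.
- New illness, with a condition on dosing: "An illness, sign, symptom, or clinically significant laboratory abnormality that is detected or diagnosed after study drug administration".
- Events outside the treatment period, with a condition on their cause: "Pretreatment or post-treatment events that occur as a result of protocol-mandated procedures".

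The list of what is not an AE covers the disease under study unless it worsens, and pre-existing conditions that do not worsen. It does not mention new illness before dosing.

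**When AEs are recorded (section 9, Procedures for Reporting Adverse Events).** "Adverse events will be recorded from the signing of informed consent through the last dose of study drug". For serious events, the window starts at the same point and runs to 30 days beyond the final dose. The log captures start and stop dates, and seriousness is recorded as an attribute of an AE. Appendix E, footnote C, also starts monitoring at consent, but runs it through Study Visit 11 for AEs.

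**The design (section 5).** Patients are randomised "to begin teduglutide treatment immediately or to continue standard of care (SOC) treatment", and switch at Day 56. The second period ends at Day 112.

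**The concern.** The definition is written for a trial in which dosing follows baseline directly. Here, a SOC-first patient has had no study drug for the whole of the first randomised period, so that period is pretreatment under the definition. The only item for new illness needs prior dosing, and the only item that mentions pretreatment events needs a procedural cause. A new illness that no procedure caused, arising in a SOC-first patient between Day 0 and Day 56, fits neither. The same illness in a teduglutide-first patient's SOC period fits the new-illness item, because drug has already been given.

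Whether a control-period event is classified as an AE could therefore depend on sequence. Safety is a stated objective and part of the hypothesis. The SOC-first Days 0 to 56 are the only randomised control time not preceded by teduglutide, so they are the natural background against which on-drug events would be read. Background events are expected: the section on withdrawal says readmissions for fistula-related complications are common. Section 7 has no safety analysis and no rule for assigning AEs to a treatment period, so nothing later in the plan would correct uneven classification.

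**Working it through.** The plan gives no figure on this point, so there is none to reproduce. The check has two parts.

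**1. The passages side by side, for a new illness that no procedure caused, with onset in a SOC period**

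| Rule | SOC-first, Days 0–56 | Teduglutide-first, Days 56–112 |
|---|---|---|
| New-illness item (section 9) | Not met: no drug given yet | Met: after drug |
| Pretreatment/post-treatment item (section 9) | Not met: no procedural cause | Not met: no procedural cause |
| AE recording window (section 9) | Inside: after consent, before last dose | Outside, unless the patient enters the extension: last dose is about Day 56 |
| AE monitoring window (Appendix E, footnote C) | Inside | Inside |

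The SOC-first control period lies inside both recording windows but outside the literal new-illness item. That is the contradiction. The last two rows of the right-hand column show a second one: whether the other half of the control time is recorded depends on which AE end date applies.

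**2. How much control time is exposed**

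Inputs: 10 patients (section 2, Design); 56 days per period (section 5). The allocation ratio is not stated. I assume 5:5 and show 3 to 7 SOC-first patients. Under simple 1:1 randomisation that range has probability (120 + 210 + 252 + 210 + 120)/1024 = 0.89.

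- Planned SOC time: 10 × 56 = 560 patient-days.
- SOC-first share: 5 × 56 = 280, and 280/560 = 50%. With 3 SOC-first patients, 168/560 = 30%; with 7, 392/560 = 70%.

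Coverage of SOC time at 5:5, ignoring extension dosing:

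| Rule applied | SOC patient-days covered |
|---|---|
| Footnote C window, AEs counted from consent | 560/560 = 100% |
| Footnote C window, new-illness item read literally | 280/560 = 50% (teduglutide-first half) |
| Section 9 AE window, AEs counted from consent | 280/560 = 50% (SOC-first half) |
| Section 9 AE window, new-illness item read literally | 0/560 = 0% |
| Section 9 SAE window, events counted from consent | (280 + 5 × 30)/560 = 430/560 = 76.8% (67.5% to 86.1% for 3 to 7 SOC-first) |

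The two problems affect opposite sequences. Correcting only the end date restores the teduglutide-first half. Correcting only the definition restores the SOC-first half. Both corrections are needed for full coverage.

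**The case against.** The strongest reply is that the definition is not exclusive. The list says what an AE includes, which can be read as examples. The general wording reaches marketed as well as investigational products, and SOC patients receive marketed products. The list of exclusions does not name pre-dose illness. Exacerbations count whatever the dosing, and many fistula complications could enter that way or as worsening of the disease studied. Clinically significant laboratory and examination findings have their own reporting route with no dosing condition. Recording starts at consent, and AE questions are scheduled at every contact from Day 7 in both sequences.

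Most of this stands, and it limits the size of the point. It does not remove the point. The consent start says when AEs are recorded, not what counts as one. If every pretreatment event counted anyway, the procedural qualifier would do no work. The separate route for examination findings relies on scheduled examinations, while section 5 lets some SOC visits be replaced by telephone calls. SAEs are not clearly protected either, because seriousness is handled as an attribute of an AE.

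A reader might go further and infer that these events are definitely not AEs, that half of the control safety data is lost, and that teduglutide would appear to have twice the SOC event rate (560/280 = 2.0). The documents do not support this. The 50% is planned person-time under an assumed split. The ratio needs no capture at all in the SOC-first period, full capture in the teduglutide-first SOC period (which holds only under footnote C's end date, or for patients who enter the extension), equal and constant rates, and uncounted days kept in the denominator. Section 7 plans no comparison of AE rates, so no such ratio would be produced.

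**Conclusion.** The point holds as a conflict of wording that carries a risk of uneven classification. The new-illness item does not fit a cross-over with a SOC-first sequence, and it contradicts the consent-based start stated in section 9 and in footnote C. Staff who apply it literally may leave new, non-procedural illnesses in SOC-first patients' Days 0 to 56 unclassified as AEs, while classifying the same events in the other sequence.

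The exposed time is at most 280 of 560 planned SOC patient-days at 5:5, or 30% to 70% for 3 to 7 SOC-first patients. This assumes full 56-day periods and a literal reading. It does not measure events lost, and no bias in a rate ratio can be derived from it. Importance is minor to moderate. It should be corrected because safety is an objective, the trial is small, and the remedy is nearly free.

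**What to change.** 1. In the section 9 definition, change the time condition of the new-illness item from after dosing to after consent, so that it applies equally to both sequences.
2. In the item on events before and after treatment, state that pretreatment events count whether or not a study procedure caused them.
3. In section 7, add that each AE is tabulated by the period in which it began (pre-randomisation, SOC or teduglutide), using the start date already recorded. Show follow-up and extension time separately where it is included.
4. Reconcile the AE end date in section 9 (last dose) with footnote C (Study Visit 11). Do this in the same amendment, because recording in the teduglutide-first SOC period depends on it.

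The cost is a few sentences of protocol text. No extra visits or data are needed, since AEs are already asked about at each contact and start dates are already logged. For patients already enrolled, the SOC-first period should be checked against source notes for events noted but not classified.
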